8.3. Analysis Populations

8.3.1. Enrolled Population

The enrolled population includes all subjects who complete the informed consent.

8.3.2. Safety Population

The safety population includes all subjects who receive any amount of study drug.

8.3.3. Efficacy Population

The efficacy population includes all subjects who receive any amount of study drug, and have a baseline and at least one post-baseline 24-hour urine protein.

9. DATA PRESENTATIONS AND DATA MANAGEMENT

9.1. Data Presentations

The plan for tabular presentations and analysis of the data, in general, is divided into five categories:

1. Subject disposition using the enrolled population.
2. Baseline and demographic profile using the safety population.
3. Analyses of the efficacy data using the efficacy population.
4. Safety and tolerability using the safety population.
5. Analyses of PK, PD and ADA.

9.2. Data Management

All statistical analyses will be performed using SAS version 9.4 or later (SAS Institute Inc., Cary, NC).

10. SUBJECT DISPOSITION

The number of subjects treated, completing the protocol specified duration of study drug, discontinuing study drug early, completing the study, and early withdrawal from the study will be summarized by disease group. The reason(s) for early discontinuation of study drug and early withdrawal from the study will be summarized. The number of subjects in Cohort 1 and Cohort 2 who rollover to Cohort 3 will be summarized. A list of subjects failing any eligibility criteria will be provided.

11. BASELINE SUBJECT DATA

11.1. Baseline Demographic and Subject Characteristics

The following demographic and subject characteristics will be summarized by disease group, cohort and treatment: Age at informed consent, gender, ethnicity, race, duration of disease, weight, BMI, positive anti-PLA-2R antibody (MN subjects in Cohort 1 only), baseline 24-hour urine protein, baseline urine albumin/creatinine ratio, baseline dose of prednisone (mg per day, Cohort 1 only), baseline use of immunosuppressive treatment and baseline eGFR.

Concomitant medications used at baseline will be listed.

11.2. Medical History and Physical Examination

A listing of reported medical and surgical history, and physical examination at screening will be provided.

12. EFFICACY ANALYSIS

12.1. General Considerations

All data summaries will be descriptive in nature and efficacy summaries will be presented by disease group, cohort and treatment. Summary statistics for continuous variables will include number of subjects, mean, median, standard deviation, minimum, and maximum. For categorical variables, frequencies and percentages will be provided. Baseline value will be calculated according to Section 8.3.1. All confidence intervals will be constructed at the two-sided 95% confidence level.

The data collected during the re-treatment period for the rollover subjects in Cohort 1 and Cohort 2 will be presented in listings. Because the open-label OMS721 dose is different from the original OMS721 dose and re-treatment is optional, statistical analyses for Cohort 1 and Cohort 2 will include the data collected in the initial treatment period and the initial follow-up period only. Statistical analyses for Cohort 3 will include the subjects who are randomized in Cohort 3 only. All data collected for the randomized subjects in Cohort 3 will be summarized.

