5. OMS721 PK
6. OMS721 PD
7. Urine protein/creatinine ratio change from baseline to 12 weeks by disease
8. Change from baseline in serum creatinine by disease
9. Change from baseline in eGFR calculated using the following equations by disease state: MDRD equation, CKD-EPI using serum creatinine, CKD-EPI using cystatin C, and CKD-EPI using creatinine – cystatin C
10. Occurrence of ADA and NAb
11. Urine inflammatory markers by disease
12. Duration of therapeutic response, if observed, defined as 24-hour urine protein < 50% of baseline for up to 104 weeks (Cohort 2 only)

Statistical Methods:

Sample Size Determination

The primary objective of the study is to assess safety and tolerability of OMS721. The sample size has been empirically determined for each cohort.

Analysis Populations

Safety analyses will be based on the safety population, which includes all subjects who receive any amount of study drug.

Efficacy analyses will be based on the efficacy population, which includes all subjects who receive any amount of study drug and have a baseline and at least one post-baseline 24-hour urine protein.

Statistical analyses will group subjects according to their assigned cohort, except for the rollover subjects who will constitute their own cohort.

Safety Analyses

The safety endpoints will be descriptively summarized. Adverse events will be coded according to preferred term and system/organ class using the Medical Dictionary for Regulatory Activities (MedDRA) AE coding dictionary. Laboratory tests and vital signs will be summarized by visit.

CONFIDENTIAL

No use, disclosure or reproduction outside of Omeros without prior written authorization

Efficacy Analyses

The efficacy endpoints will be descriptively summarized by visit, disease and cohort.

Pharmacokinetic Analyses

Serum drug concentration will be summarized by visit, disease, and cohort. Non-compartmental models will be used to estimate the PK parameters. ADA information will be summarized by visit.

CONFIDENTIAL

No use, disclosure or reproduction outside of Omeros without prior written authorization

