8.2. Subject Exclusion Criteria

Subjects will be excluded from the study for any of the following reasons:

1. Have a known hypersensitivity to any constituent of the investigational product.
2. Have a hemoglobin < 9.0 g/dL.
3. Have a platelet count < 100,000/mm³.
4. Have an absolute neutrophil count < 500 cells/mm³.
5. Have an ALT or AST > 3.0 x the upper limit of normal.
6. Have systemic manifestations of Henoch-Schonlein purpura (e.g., joint pain, gastrointestinal bleeding, abdominal pain) within 2 years prior to Screening Visit 1.
7. Have used belimumab, eculizumab, or rituximab within 6 months of Screening Visit 1.
8. Have a history of renal transplant.
9. Have a diagnosis of human immunodeficiency virus (HIV), hepatitis B, or hepatitis C infection or positive serology at Screening Visit 1 for HIV, hepatitis B, or hepatitis C.

CONFIDENTIAL

No use, disclosure or reproduction outside of Omeros without prior written authorization

10. Have any significant infection requiring antibiotic treatment at Screening Visit 1.
11. Have a malignancy except for adequately treated and cured basal or squamous cell skin cancer, curatively treated *in situ* disease, or other cancer from which the patient has been disease-free for ≥ 5 years.
12. Have an expectation of survival of less than 24 months.
13. If female, are pregnant or breastfeeding.
14. Have received any other investigational drug or device or experimental procedures within 30 days of Screening Visit 1.
15. Are an employee of Omeros, the investigative site, a study staff member, or their immediate family member.
16. Have any condition that the Investigator believes would put the subject at risk from participation.
17. For subjects in Cohort 2 and Cohort 3, have received corticosteroids within the 3 months prior to screening. Subjects in Cohort 1 rolling into Cohort 3 must have IgAN and must have discontinued corticosteroids prior to entry into Cohort 3, but the discontinuation may occur at any time prior to Cohort 3 entry.

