10.2. Concomitant Therapy

Belimumab, eculizumab, and rituximab are not to be used during the study. For subjects in Cohort 2 and Cohort 3, treatment with corticosteroids is prohibited during the study except inhaled corticosteroids and short-term use of corticosteroids that are not being used for the management of IgAN. All other medications for the health and well-being of the subject are permitted and are to be recorded.

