13.2.1. General Considerations

All data summaries will be descriptive in nature and summaries will be by disease and cohort, additionally safety information will be summarized overall for all subjects. Summary statistics for continuous variables will include number of subjects, mean, median, standard deviation, minimum, and maximum. For categorical variables, frequencies and percentages will be provided. When required for the statistical analysis of a particular variable, the baseline value will be the last recorded value prior to the administration of the first dose of study treatment. The exception is the urine albumin/creatinine and protein/creatinine ratios (Section [13.2.5](#)).

Statistical analyses will group subjects according to their assigned cohort, except for the rollover subjects who will constitute their own cohort.

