4. STUDY DESIGN

This is a Phase 2, multicenter study of OMS721 in subjects with the following diseases: IgAN, lupus nephritis, MN, or C3 glomerulopathy including dense deposit disease. Three cohorts will be enrolled:

- Cohort 1 will be subjects with corticosteroid-dependent IgAN, LN, MN, or C3 glomerulopathy. All Cohort 1 subjects will be receiving a corticosteroid dose of > 10 mg of prednisone or equivalent dose for at least 12 weeks. Cohort 1 subjects will all receive OMS721 4 mg/kg intravenously (IV) once weekly for 12 weeks.
- Cohort 2 will be subjects with IgA nephropathy who are not receiving corticosteroids. Cohort 2 subjects will receive either OMS721 4 mg/kg IV treatment or 5% dextrose in water (D5W) vehicle once weekly for 12 weeks in a randomized double blind design.
- Cohort 3 will be subjects with IgA nephropathy who are not receiving corticosteroids. Subjects in Cohort 3 will receive either OMS721 370 mg IV or 5% dextrose in water (D5W) vehicle in a randomized double blind design. Regardless of treatment assignment, subjects in Cohort 3 will be eligible for additional open-label OMS721 treatment if they fail to achieve a 24-hour urine protein < 50% of baseline or their 24-hr urine protein is > 1000mg/24-hours after 12 weeks of dosing [plus a 6-week follow-up period].

Cohorts 1 and 2 are ongoing at the time of Protocol Amendment 02. Upon approval of this amendment, subjects with IgAN in Cohort 1 and subjects in Cohort 2 who have started study drug and are on study will be offered the opportunity to roll into Cohort 3 for extended treatment and long-term follow-up. Subjects have to sign an informed consent and meet the eligibility criteria in order to participate in Cohort 3. The rollover subjects will not be randomized and will receive open-label OMS721 370 mg IV once per week for the remaining treatment period of their original cohort. Following rollover they will follow all study procedures for Cohort 3. Subjects with IgAN in Cohort 1 must have discontinued corticosteroids in order to roll into Cohort 3. Subjects with LN, MN or C3 glomerulopathy in Cohort 1 are not eligible rollover to Cohort 3.

Approximately 44 subjects will be enrolled (16 in Cohort 1, 10 in Cohort 2, and 18 in Cohort 3) from up to approximately 15 investigative sites.

For all subjects in Cohort 1 and Cohort 2, the study will consist of screening (4 weeks), treatment (12 weeks), and follow-up (6 weeks) periods.

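### SAP 12.1 sets no cut at Cohort 3 entry, so a Cohort 2 vehicle subject who rolls over mid-course onto open-label OMS721 still counts as vehicle

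*SAP*

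**What the plan says.** **Rollover.** Protocol 7.1 and SAP 4 let Cohort 2 subjects, and Cohort 1 subjects with IgAN, move into Cohort 3 once they have started study drug. They are not randomized. They "will receive open-label OMS721 370 mg IV once per week for the remaining treatment period of their original cohort" and then follow Cohort 3 procedures. Re-treatment is something else: a separate course (RT1 to RT12, SAP 5.2), available from the 6-week follow-up visit onward, in weeks 18 to 91.

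**Grouping.** Protocol 13.2.1, repeated in the synopsis, says: "Statistical analyses will group subjects according to their assigned cohort, except for the rollover subjects who will constitute their own cohort". SAP 12.1 has no rollover cohort. It sends rollovers' re-treatment data to listings and then gives a reason, "Because the open-label OMS721 dose is different from the original OMS721 dose and re-treatment is optional", and a rule, "statistical analyses for Cohort 1 and Cohort 2 will include the data collected in the initial treatment period and the initial follow-up period only". For the remaining cohort it says: "Statistical analyses for Cohort 3 will include the subjects who are randomized in Cohort 3 only". SAP 21.1, which records changes from the Protocol, lists only the clarified definition of response duration.

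**Analyses affected.** For Cohorts 2 and 3, SAP 12.6 to 12.8 give the OMS721-minus-vehicle mean difference with a 95% confidence interval at each visit, for 24-hour urine protein, the two urine ratios and eGFR. SAP 12.9 summarizes change in Cohort 1 corticosteroid dose by visit and disease. None of these sections has a rule for rollovers.

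**Steroids.** A Cohort 1 subject who rolls over "must have discontinued corticosteroids prior to entry into Cohort 3, but the discontinuation may occur at any time prior to Cohort 3 entry" (Protocol 8.2, criterion 17). Protocol 10.2 adds: "For subjects in Cohort 2 and Cohort 3, treatment with corticosteroids is prohibited during the study except inhaled corticosteroids". Short-term use for reasons other than IgAN is also exempt. Cohort 1 has no such ban.

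**The concern.** The Protocol and the SAP place the same subjects in different groups, and the SAP does not declare the difference. The SAP rule also misses its own aim. It limits the data because the open-label dose differs from the original one, yet open-label 370 mg given in the rest of the first 12 weeks falls inside the period that it keeps.

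Most is at stake in Cohort 2, the smaller of the two randomized comparisons. After a mid-course rollover, a vehicle subject takes the active drug. The SAP does not say that treatment is assigned visit by visit, so the subject remains in the vehicle column and enters a difference that is presented as OMS721 against vehicle.

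Less is at stake in Cohort 1. The secondary endpoint is the steroid dose needed to keep renal function stable, and there is no control group. A zero recorded after Cohort 3 entry is somewhat weaker evidence of need than a zero recorded under Cohort 1 rules, and SAP 12.9 does not separate them.

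**Working it through.** The plan gives no figure to reproduce here. The check compares scopes and counts visits.

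**1. Which open-label visits stay in.** Re-treatment cannot begin before the 6-week follow-up visit (week 18). Open-label doses between rollover and T12 are therefore initial-treatment data, and FU1 and FU2 are initial follow-up. All of them fall within the SAP 12.1 rule for Cohorts 1 and 2.

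**2. Cohort 2, visits per rollover.** The schedule (Protocol 19.2) gives these post-baseline visits in the initial periods:
- urine ratios: T5, T9, FU1, FU2 (4)
- creatinine and cystatin C for eGFR: T2, T3, T4, T8, FU1, FU2 (6)
- 24-hour protein: FU2 (1). Protocol 10.1.9 supplies this collection to Cohort 3 subjects only, while the schedule has no such limit, so it is unclear how many Cohort 2 subjects contribute.

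Samples at the entry visit are taken before the dose, so only later visits are counted. T2 is the earliest possible entry, because study drug must have started.

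| Entry at | 370 mg doses, of 12 | Ratio visits, of 4 | eGFR visits, of 6 | 24-hour protein, of 1 |
|---|---|---|---|---|
| T2 | 11 | 4 | 5 | 1 |
| T6 | 7 | 3 | 3 | 1 |
| T9 | 4 | 2 | 2 | 1 |
| T12 | 1 | 2 | 2 | 1 |

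FU1, the ratio visit nearest the 12-week endpoint, is affected in every row.

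**3. Cohort 2, possible dilution (illustration only).** About 10 subjects randomized 1:1 gives about 10/2 = 5 on vehicle. Suppose that the true difference is D, that r of the 5 vehicle subjects have rolled over, that each shows a fraction f of the drug effect by that visit, and that they are otherwise typical. The expected difference is then D × (1 − r × f / 5).
- r = 1: f = 0.5 gives 0.90 D and f = 1 gives 0.80 D.
- r = 2: f = 0.5 gives 0.80 D and f = 1 gives 0.60 D.
- r = 0: no change.

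The documents give neither r nor f.

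**4. Dose change for subjects already on 4 mg/kg.** 370/4 = 92.5 kg is the only weight at which the doses agree. The following weights are assumptions:
- 60 kg: 4 × 60 = 240 mg, and 370/240 = 1.54.
- 80 kg: 320 mg, and 370/320 = 1.16.
- 100 kg or more, with the cap in SAP 13.3: 400 mg, and 370/400 = 0.925.

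SAP 13.3 still computes the intended dose for Cohorts 1 and 2 at 4 mg/kg, with no rule for 370 mg.

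**5. Cohort 1 steroid dose, visits per IgAN rollover.** Dose is recorded at T2 to T12 (11 visits), FU1 and FU2, which makes 13.
- Entry at T6: 7 + 2 = 9, and 9/13 = 69%.
- Entry at T9: 4 + 2 = 6, and 6/13 = 46%.
- Entry at T12: 1 + 2 = 3, and 3/13 = 23%.
- Without the entry visit: 8, 5 or 2 of 13 (62%, 38%, 15%).

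These are upper bounds. The taper starts at T5 and runs four weeks, so entry at T6 would need zero steroid within about a week of starting it.

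**The case against.** SAP 12.1 nowhere says that post-rollover visits stay in Cohorts 1 and 2. That follows only from the missing cut. The stated reason suggests that the sponsor meant to keep open-label data out, and perhaps read the initial periods that way. The study is descriptive, unpowered and without formal tests. Rollovers are counted (SAP 10), dosing is listed (SAP 13.3), and Protocol 13.2 promises that changes in method will appear in the study report. Much of this stands: the defect is an undefined boundary rather than a stated decision to pool. But whoever programs the tables has to choose a side, the literal text keeps the visits, and listings do not correct a summary difference or its interval.

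The documents do not support three stronger readings that a reader might infer:
- **That all of the rollovers' open-label data are pooled.** Re-treatment data are expressly confined to listings. Only initial-period visits are at issue.
- **That the Cohort 3 ban produces the steroid-free results in Cohort 1.** Steroids must already be stopped before entry, so the first zero arises under Cohort 1 rules. A restart would still be recorded and analyzed, so the ban can only discourage one. The taper target is 6 mg or less, not zero, so few may qualify. For entry at T9 or later, results through the taper are untouched, apart from the entry visit.
- **That rollovers should be moved wholly out of Cohort 1, as a literal reading of the Protocol suggests.** This would remove subjects selected for being off steroids and distort the steroid summary in the other direction.

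**Conclusion.** The concern holds for initial-period visits after a mid-course rollover. SAP 12.1 leaves them in the Cohort 1 and Cohort 2 summaries, against Protocol 13.2.1 and against its own reason, and SAP 21.1 does not say so.

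The main effect is in Cohort 2, where open-label OMS721 data can be counted as vehicle. If the planned split is 5 and 5, one such subject is 20% of the vehicle group. Under the assumptions in step 3, the expected difference would then be up to 20% smaller if OMS721 works. OMS721-arm rollovers also change dose, with an effect of unknown direction, so no net bias is claimed.

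The steroid point in Cohort 1 is secondary: some later zeros are weaker evidence of need, with no size or direction established. The number of mid-course rollovers is not given for either cohort. If it is zero, nothing in the summaries changes and only the documentation gap remains.

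**What to change.** - **SAP 12.1:** derive a flag from the Cohort 3 entry date for every visit after entry. End the Cohort 2 OMS721-versus-vehicle summaries (SAP 12.6 to 12.8) at entry for each rollover, with n at each visit. Summarize post-entry visits as a separate rollover group, which serves the Protocol's intent.
- **SAP 12.9:** keep the all-subjects Cohort 1 IgAN steroid table and add a version cut at entry, with n at each visit.
- **SAP 21.1:** list the grouping as a change from the Protocol.

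The cost is some wording, one derived flag and a few extra tables. No new data are needed. The downside is very small groups. After entry, the cut tables hold only non-rollovers, who are a selected set, so the cut tables should be read beside the all-subjects tables and not replace them.

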12.2. Testing Statistical Assumptions Including Comparability at Baseline

The efficacy objective of this study is to estimate the effect of OMS721. Baseline characteristics will not be compared among the disease groups and study treatment.

12.3. Statement of the Null and Alternate Hypotheses

The efficacy objective of this study is to estimate the effect of OMS721. Formal statistical tests will not be performed.

12.4. Subgroup Analyses

All analyses will be performed by disease group, cohort and treatment. Due to the small sample size of the study, subgroup analysis is not planned.

12.5. Multiple Comparisons and Multiplicity

Not applicable.

12.6. Analysis of 24-hour Urine Protein

Change from baseline in 24-hour urine protein and change from baseline in natural log transformed 24-hour urine protein will be summarized descriptively for each visit by disease, cohort and treatment. Ninety-five percent confidence intervals (CIs) for the mean change in both the original value and the log-transformed value will be provided for each visit using t-distribution. For Cohort 2 and Cohort 3, the mean difference between OMS721 and vehicle and its 95% CI will also be provided for each visit using t-distribution.

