9.1.2. Blinding

Cohort 1

No blinding is necessary for Cohort 1 since all subjects receive OMS721.

Cohort 2 and Cohort 3

Subjects in Cohort 2 and Cohort 3 will be randomized in a 1:1 fashion to receive either OMS721 or D5W vehicle control during the first 12 treatment weeks. Randomization for Cohort 3 will be stratified by region: North American and the United Kingdom in one strata and Asia in another strata. Study drug administration will be blinded. Additional treatment courses after the first 12 weeks in Cohort 3 will be open-label OMS721.

Treatment assignment will be blinded to all trial personnel, Omeros and its representatives, with the following exceptions:

- Investigative site pharmacist or designee who responsible for maintaining the blind at the site and will prepare and label the infusion.
- An independent site monitor (Clinical Research Associate), who will only monitor study drug accountability.
- Omeros CMC representative who will manage drug supply
- Omeros clinical data manager overseeing the implementation of the randomization module

In a medical emergency, it may be necessary to identify a subject's assigned treatment before the study has been completed and treatments unblinded. The treatment blind should only be broken if this information is necessary to treat the subject for a medical condition. In this situation, it is important that the treatment blind be maintained for all other subjects. The Omeros Medical Monitor should be contacted immediately if the treatment blind is broken. The date and reason for breaking the blind must be discussed with the Omeros Medical Monitor and recorded in the source documents.

CONFIDENTIAL

No use, disclosure or reproduction outside of Omeros without prior written authorization

Unblinding a subject's treatment assignment by the Investigator or study site personnel under any other circumstances (except as noted above) will be considered a protocol deviation.

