Cohort 3 subjects who have 24-hour urine protein > 1000 mg anytime between weeks 18-91 or 24-hour urine protein \geq 50% of baseline during the follow-up period may elect, with the agreement of the Investigator, to receive open-label OMS721 370 mg IV for 12 weeks. Additional 12-week OMS721 treatment courses may be administered as often as subjects have 24-hour urine protein > 1000 mg or 24-hour urine protein \geq 50% of baseline during weeks 18-91. The visit schedule for each series of additional OMS721 treatment is provided below. If a subject receives re-treatment, the subject's re-treatment visit schedule will be followed until the re-treatment follow-up is completed (see below for re-treatment schedule). At that time, the subject's next visit will be at the first regularly scheduled follow-up visit following the initial OMS721 treatment course.

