10.1.12. Cohort 3 Re-Treatment Visit 1 RT1 (+/- 2 days)

Prior to re-treatment visit 1, subject eligibility for re-treatment must be confirmed. OMS721 will be administered to all subjects undergoing re-treatment.

Prior to administering the dose of study drug the following procedures will be performed:

1. Review of AEs and concomitant medications.
2. Vital signs including BP, pulse rate, RR, and temperature (after at least 5 minutes of rest).
3. ECG taken (after at least 5 minutes of rest in the supine position)
4. Laboratory samples will be collected for:
 - Hematology, chemistry, coagulation, cystatin C
 - Urinalysis
 - Urine for inflammatory biomarkers
 - Serum or urine pregnancy test in women of childbearing potential. If the test result is positive then the subject will be excluded from further treatment, but continue follow-up
 - Blood samples for future research
 - Serum PK sample

CONFIDENTIAL

No use, disclosure or reproduction outside of Omeros without prior written authorization

- Serum PD sample
- Serum ADA sample

Study drug will be administered by IV infusion over 30 minutes.

After dosing with study drug, the following procedures will be performed:

1. Vital signs including BP, pulse rate, RR, and temperature (after at least 5 minutes of rest) at the following timepoints: 30 minutes, 1 hour.
2. ECG taken (after at least 5 minutes of rest in the supine position), to be obtained immediately post dose).
3. Serum PK samples at the following timepoints after end of dosing: 5 minutes, 2 hours, and 24 hours (**Day 2**), 72 hours (**Day 4**).
4. Serum PD sample after the end of dosing: 2 hours.
5. The subject may be discharged after arrangements are made for the collection of PK samples on **Days 2 and 4**.

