8.2.3. Visit Windows Relative to the First Dose of Study Treatment

Table 2: Visit Windows (Days)

Visit	Target Day	Visit Window (Days) ¹
Day -28 (Screening Visit 1)	-28	-28 to -21
Day -14 (Screening Visit 2)	-14	-20 to -1
Day 1 (Treatment Visit 1)	1	1
Day 2 (Treatment Visit 1) ²	2	2 to 3
Day 4 (Treatment Visit 1) ²	4	4
Day 8 (Treatment Visit 2)	8	2 to 11
Day D (Treatment Visit T, T>2)	D (15, 22, ..., 78)	D – 3 to D + 3
Day 85 (Follow-up Visit 1)	85	82 to 102
Day 120 (Follow-up Visit 2)	120	103 to 148
Day 176 (Follow-up Visit 3)	176	149 to 221
Day 267 (Follow-up Visit 4)	267	222 to 312
Day 358 (Follow-up Visit 5)	358	313 to 403
Day 449 (Follow-up Visit 6)	449	404 to 494

Table 2: Visit Windows (Days) (Continued)

Visit	Target Day	Visit Window (Days) ¹
Day 540 (Follow-up Visit 7)	540	495 to 585
Day 631 (Follow-up Visit 8)	631	586 to 676
Day 722 (Follow-up Visit 9)	722	≥ 677

¹ If there are more than 1 non-missing assessments in the same visit window, the closest one to the target day will be used in the analysis. If there are 2 assessments that are equally spaced from the target day, the latter will be used in the analysis.

² Day 2 and Day 4 apply to PK only.

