12.7. Analysis of Urine Albumin/Creatinine Ratio and Urine Protein/Creatinine Ratio

The analysis value for urine albumin/creatinine ratio and urine protein/creatinine ratio is defined as the average of all the values obtained for a timepoint. The planned number of urine albumin/creatinine ratios and urine protein/creatinine ratios is three at each scheduled timepoint. The baseline value of the urine albumin/creatinine ratio and urine protein/creatinine ratio is defined as the average of the analysis values at the two screening visits, i.e.,

$$\text{Baseline urine albumin/creatinine ratio} = (R_1 + R_2)/2,$$

R_1 and R_2 are the average values at screening visits 1 and 2, respectively. The baseline urine protein/creatinine ratio is defined in the same fashion.

Change from baseline and change in natural log transformed analysis value of urine albumin/creatinine ratio and urine protein/creatinine ratio at each scheduled visit will be summarized descriptively for each disease group, cohort and treatment. Nine-five percent CIs for the mean change in both the original value and the log transformed value at each scheduled visit will be provided using t-distribution. For Cohort 2 and Cohort 3, the mean difference between OMS721 and vehicle and its 95% CI will also be provided for each visit using t-distribution.

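### After Week 18 the by-visit OMS721-minus-vehicle differences in Cohort 3 mix in open-label OMS721, and the visit windows, applied as written, label re-treatment values as Follow-up Visits 3 to 9

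*SAP*

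**What the plan says.** - **Contrast.** For 24-hour urine protein, SAP 12.6 plans: "For Cohort 2 and Cohort 3, the mean difference between OMS721 and vehicle and its 95% CI will also be provided for each visit". SAP 12.7 (urine albumin/creatinine and protein/creatinine ratios) and 12.8 (eGFR) carry the same sentence: "the mean difference between OMS721 and vehicle and its 95% CI will also be provided for each visit using t-distribution". None of the three sets a last visit for the contrast.
- **Data included.** SAP 12.1 limits Cohorts 1 and 2 to initial treatment and initial follow-up, because the open-label dose differs and re-treatment is optional. For Cohort 3 it says: "All data collected for the randomized subjects in Cohort 3 will be summarized".
- **Who can be re-treated.** SAP 4: "Regardless of treatment assignment, subjects in Cohort 3 will be eligible for additional open-label OMS721 treatment". Protocol 9.1.2: "Additional treatment courses after the first 12 weeks in Cohort 3 will be open-label OMS721". Protocol 10.1.12: "OMS721 will be administered to all subjects undergoing re-treatment". The trigger is 24-hour protein above 1000 mg or at least 50% of baseline, from Week 18 to Week 91, and courses can be repeated.
- **Visits during re-treatment.** Under Protocol 10.1.11, the subject's "re-treatment visit schedule will be followed until the re-treatment follow-up is completed"; regular follow-up then resumes.
- **Windows.** SAP 8.2.3, Table 2, counts days from first dose, has no rows for RT1-RT12 or the re-treatment follow-up visit (RTFU), and assigns every day from 149 onward to one of Follow-up Visits 3-9. When a window holds several values, "the closest one to the target day will be used in the analysis", whatever the subject's treatment status.

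**The concern.** A difference headed OMS721 versus vehicle will be read as the effect of the blinded course. From Week 26 on, some of the vehicle arm may have had 12 or more open-label doses of OMS721, and so may some of the OMS721 arm. Entry required more than 1000 mg/24 hours, so a vehicle subject whose proteinuria has not changed meets both limbs of the re-treatment trigger. If the drug works, vehicle subjects are the more likely to qualify, and a shrinking late difference could be mistaken for a fading effect of the first course.

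The windows add a second problem. A value taken during, or one week after, an open-label course can appear in a row named for an extended follow-up visit, under the randomised arm, with nothing to show that the subject had been re-treated.

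**Working it through.** The plan gives no power, SD, effect size or re-treatment rate, so there is no stated figure to reproduce. Three checks apply.

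**1. Which 24-hour protein visits precede open-label drug.** The SAP 5.1 schedule collects post-baseline 24-hour urine at Follow-up Visit 2 (Day 120) and at Follow-up Visits 3-9: 1 + 7 = 8 collections. Re-treatment opens on the Follow-up Visit 2 result, so 7 of the 8 come after it opens.

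**2. Where re-treatment visits fall in Table 2.** SAP 5.2 puts RT5, RT9 and RTFU on re-treatment days 29, 57 and 85. With RT1 on study day s, they fall on s+28, s+56 and s+84 (planned days, ignoring tolerances). The documents give no interval from the qualifying value to RT1, so s is an assumption.

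| RT1 (day s) | RT5 | RT9 | RTFU | Window holding RTFU |
|---|---|---|---|---|
| 127 | 155 | 183 | 211 | Follow-up Visit 3 (149-221) |
| 134 | 162 | 190 | 218 | Follow-up Visit 3 |
| 137 | 165 | 193 | 221 | Follow-up Visit 3 |
| 138 | 166 | 194 | 222 | Follow-up Visit 4 (222-312) |

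- 24-hour protein is collected in re-treatment only at RTFU. For s from 121 to 137, that value is the one available for Follow-up Visit 3, one week after the twelfth open-label dose, because the re-treatment schedule displaces the Day 176 visit.
- For eGFR and the ratios with s = 127, the distances from Day 176 are 21 (RT5), 7 (RT9) and 35 (RTFU), so the mid-course RT9 value is selected.
- If RT1 is 7 days after any of Follow-up Visits 3-8, RTFU comes 7 + 84 = 91 days after that visit. That is the spacing of the extended visits, so RTFU lands on the next target day (267, 358, 449, 540, 631 or 722).
- The urine-ratio kit is not scheduled at Follow-up Visits 3-9. Any ratio value in those windows can come only from a re-treated subject.

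**3. How much of the difference could remain.** Assume no mean change on vehicle, normally distributed log change, and the 50%-of-baseline limb alone. The eligible share of vehicle subjects is 1 − Φ(ln 0.5/SD) = 0.96, 0.92 and 0.88 for SD 0.4, 0.5 and 0.6.

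- *Assumption A: re-treated vehicle subjects reach the OMS721 level and the OMS721 arm does not change.* Retained share = 1 − eligible × uptake. At full uptake this is 1 − 0.96 to 1 − 0.88, or 4-12%. At half uptake it is 52-56%.
- *Assumption B: each course adds the same log effect in either arm.* Retained share = 1 − uptake × (vehicle eligible − OMS721 eligible). With SD 0.5, the OMS721 share eligible is 1 − Φ((ln 0.5 − ln 0.7)/0.5) = 0.75 for a true 30% reduction, and 0.50 for a 50% reduction. At full uptake, 1 − (0.92 − 0.75) = 83% and 1 − (0.92 − 0.50) = 58%.

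For scale, with 18 subjects randomised 1:1 the 95% CI half-width is t(0.975, 16) × √(2/9) = 2.12 × 0.471 ≈ 1.0 SD.

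**The case against.** **Little of importance rests on these rows.** This largely stands. The primary endpoint is safety. The secondary proteinuria and albumin/creatinine endpoints are changes to 12 weeks, and both interim analyses come at the end of the 6-week follow-up. The study is not powered for comparisons and plans no formal tests. Duration of response has its own within-subject endpoint. A reader might infer that the late contrast is how the plan answers the durability question; the documents do not support that.

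**The SAP does not say that re-treatment values become follow-up visits.** Also true. SAP 5.2 gives re-treatment its own visit names and day count, the table shells are a separate document that might handle it, and SAP 12.7 summarises ratios at scheduled visits, which could leave the late ratio rows empty. But Table 2 is the only windowing rule, and as written it captures those values.

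**The Follow-up Visit 3 example depends on a prompt start.** Correct. From Day 138, RTFU moves to the Follow-up Visit 4 window, where an on-time regular visit could be nearer the target. The Follow-up Visit 3 value would then be missing rather than diluted. The later regular values would still follow open-label treatment, so better windows alone do not repair the contrast.

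**Comparing arms as randomised, with optional open-label treatment, is legitimate.** It is, but the SAP does not say that this is what it estimates; it names the contrast OMS721 and vehicle.

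**The near-total loss under assumption A is one-sided.** It is. OMS721 subjects may be re-treated too. One who falls from 3000 to 1200 mg is at 40% of baseline but still above 1000 mg, and so qualifies.

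**Conclusion.** The point holds and should be fixed, but it is not critical. As written, SAP 12.1, 12.6-12.8 and Table 2 together give Week 26-104 rows that are headed as drug versus vehicle yet can include open-label OMS721 in both arms, with re-treatment values carrying follow-up visit names. For 24-hour protein, Follow-up Visit 2 is the only scheduled contrast clear of open-label drug.

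The distortion is most plausibly toward zero, because vehicle subjects are the likelier to qualify if the drug works. Its size is unknown: at full uptake, 4-12% of the log difference remains under assumption A and 58-83% under B. Neither can be preferred on the documents, which give no uptake rate and no effect of a further course, and re-treatment in the OMS721 arm could alter the size or the direction. A reader might infer from A alone that the late difference nearly disappears; that would overstate what is known. The consequence is misreading of late descriptive estimates, not a type I error problem.

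**What to change.** 1. **SAP 8.2.3.** Add windows for RT1-RT12 and RTFU counted from each subject's RT1 date for each course, and exclude those assessments from the Follow-up Visit 3-9 windows.
2. **SAP 12.6-12.8.** As an estimate of the blinded-course effect, limit the OMS721-vehicle difference and its CI to visits through Follow-up Visit 2.
3. **Weeks 26-104.** Summarise change from baseline by randomised arm, with the number already re-treated at each visit. Label any arm difference as a comparison of randomised strategies with optional open-label OMS721.
4. **Split by re-treatment status.** If one is shown, keep it descriptive and note that it selects on response: the subjects not yet re-treated are enriched for responders in both arms.

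The cost is SAP wording and programming, with no new data and no change to treatment. The price is that late visits no longer provide a drug-versus-vehicle estimate.
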